The use of a multicenter study comprising more than one center, which will be several kilometers apart, will limit the possible geographical and environmental impact on the results of our sample in relation to the target population. In addition, routine screening of all patients presenting with TNS and negative EEG, in the setting of cSDH, regardless of the time of admission, will also ensure a more representative sample of the population.

In order to limit the bias of voluntarism, we have implemented several measures. First, it is important to minimize the number of patients who might decline to participate in the study. For that, we have constructed our study so that participation in the study does not involve additional testing or traveling than is already indicated by the primary pathology. In addition, we will educate patients on the equal effectiveness of the treatments that will be offered in the study and the fact that these two treatments are currently approved for the treatment of their condition. This should be reassuring. In addition, the availability of a member of the research team for any questions or side effects will also be a positive reason to participate. Ultimately, the substituted consent clause will help maintain eligibility for a significant proportion of patients, given the prevalence of confusion and neurocognitive disorder in the population with cSDH.

Measures to avoid dropouts

Once the randomization, it will be necessary to minimize the dropouts in order to maintain the random effect of the randomization and therefore a representative sample of the population. To begin with, it will be important to be readily available. Patients will have our contact details and a telephone follow-up will be carried out when problems arise. If necessary, a clinic appointment can be set. When side effects, it will be discussed with the patient to lower the dose, in order to reduce the side effects, before stopping the antiepileptic permanently. Of course, the final decision will be up to the patient.

In addition, the medication will be started in increasing doses, in order to limit side effects.

Limiting clinical appointments to what patients would have had without participating in the study, namely neurology follow-up and neurosurgery follow-up, should also limit dropouts by limiting the involvement required by patients.

Variables and data collection

Initial data

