The intervention (Topiramate versus Levetiracetam) will be initiated in the hospital and then, initially, a prescription will be given to the patient for the community pharmacy.

Topiramate will be initiated at 50 mg BID, with an expected increase of 50 mg per week until symptoms are controlled or up to a maximum titration of 100 mg BID.

Levetiracetam will be initiated at 500 mg BID, with an expected increase of 1000 mg divided into 2 doses per week until symptoms are controlled or up to a maximum titration of 1500 mg BID.

The drugs could be reduced or stopped after discussion with a doctor because of side effects or no improvement in TNS.

Follow-up

There will be two phone follow-ups (2nd week and 6th month), as well as two clinical follow-ups (2nd and 4th month).

Phone follow-up: Medical evaluation by a resident, neurologist or neurosurgeon participating in the study. The person administering the assessment will follow a standardized questionnaire so as not to omit information relevant to the study. This assessment includes characterization of transient neurological symptoms and investigation of side effects.

Clinical follow-up: The patient will bring his study notebook to the appointment, in which he will have recorded the various TNS or side effects that have occurred in recent weeks. The appointment will be made by a neurologist or a neurosurgeon (all patients will have a meeting with each of the two specialists). The doctor will therefore carry out an evaluation of TNS and side effects, by completing the standardized questionnaire, which will help to limit the missing data.

The last follow-up will take place at 6 months, a date that we have based on the various studies in cortical depression which have demonstrated maximum effectiveness of TPM at 17 weeks²³. As we did experience in our community, we believe that a significant difference could emerge even earlier.

Losses during follow-up: patients who do not come to the follow-up appointment will be contacted again. In the event of a refusal to attend follow-up or a second absence from an appointment, with the patient's consent, a medical assessment may be completed by phone.

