If the patient wishes to stop the antiepileptic drug, a trial of smaller doses of the same treatment will be offered. Upon refusal, or failure despite a reduction in doses, TPM will be offered to the patient if he had LEV and vice versa. This change of group will only be possible after 2 months from the beginning of treatment. These data will not be included in the calculation of the primary outcome, but can still be analyzed as a secondary outcome to assess whether changing patients from one group to another allows them to fully resolve the TNS. Patients who fail both treatments, or who refuse to attempt the treatment in the other group will be excluded from the remainder of the study and treatment with another antiepileptic recognized in the treatment of focal seizures as well as an usual follow-up will be offered.

Participant calendar

Table 4 – Participant calendar

Recruitment (Day 1)	Randomizatio n (After recruitment)	Phone follow-up (Week 2)	Clinic follow-up (Month 2)	Clinic follow-up (Month 4)	Phone follow-up (Month 6)
Standardized questionnaires : Epidemiological	Start of treatment	Medical assessment with	Medical assessment with	Medical assessment with	Medical assessment with
data Clinical features	EEG daily x 2 MRI if needed	standardized questionnaire	standardized questionnaire	standardized questionnaire	standardized questionnaire

Collection method

Sources: Data will be collected initially with the help of the patient's medical record. Subsequently, the rest will be completed entirely by the patient or his family. The evaluations will be guided by standardized questionnaires.

For patients with ECoG, continuous waveforms will be recorded for the entire period the electrode will be implanted, either up to the recording of 5 TNS episodes or up to 72 hours of recording.

The data will be collected double blind. The person administering the questionnaire and the person analyzing the data will not know the patient's group. In addition, a study number will be assigned to all patients during randomization and this is going to identify the patients on the questionnaires. Thus, the data will be entered into the Excel software anonymously. Following the study, the data will be kept for a period of 25 years, in a file locked with a password that will be in the research nurse's locked filing cabinet.

Data analysis

Statistics

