Statistical analysis of the various data will be done with the help of the Statistical Package for the Social Sciences (SPSS) software. Most of the data will be analyzed by members of the research team. If necessary, the statistician of the CRC (Clinical Research Center) will be consulted.

The results will be analyzed by "intension-to-treat" given the expected dropouts in the two treatment groups.

Primary outcome: To assess the efficacy of TPM compared to LEV in the treatment of TNS in the context of SDH with negative EEG. To do this, it will be necessary to compare the rate of complete resolution of symptoms between the two groups. Our study comprising two independent groups and this variable being dichotomous (resolution: yes or no), a Chi-Square test will be used. This same test will also be used to compare the response of TPM in the NESIS versus non-NESIS subgroups and the same comparison with LEV will also

be performed. Subsequently, as sub-analyzes, the decrease in the frequency, intensity and duration of episodes (continuous variables) will also be compared in the two groups using a Student's T-test after validation of assumptions underlying the test.

Secondary outcome: tolerance to the antiepileptics used. To do this, we will analyze the comparison of the dropout rate (dichotomous variable: yes or no) and the side effect rate (categorical variable) using a chi-square test.

Degree of significance

We retained a significance level corresponding to an error α of 5%, whether a value p<0.05. The accepted beta error (β) is 10%, for a power of 90%.

Missing data

Patients with a large number of missing data or not including the data necessary to calculate the primary outcome will be excluded from the study. Those with some missing data that do not allow certain calculations of secondary outcomes will be kept in the study, however, the sample sizes of these analyzes will be clarified during writing.

Oversight mechanism

An independent results and dropout rate monitoring committee will not be necessary. However, monitoring will be carried out by the project team.

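### Patients who fail both drugs or decline the other drug are removed from the study, so stopping treatment ends study follow-up even without withdrawal of consent

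*Protocol*

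**What the plan says.** All references are to the protocol.

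- **Follow-up, on stopping the drug.** A patient who wants to stop is first offered a smaller dose and then the other study drug. On timing: "This change of group will only be possible after 2 months from the beginning of treatment". On data after a switch: "These data will not be included in the calculation of the primary outcome". Then: "Patients who fail both treatments, or who refuse to attempt the treatment in the other group will be excluded from the remainder of the study". These patients receive another antiepileptic, "as well as an usual follow-up will be offered".
- **Follow-up, Losses during follow-up.** Patients who miss an appointment are contacted again. "In the event of a refusal to attend follow-up or a second absence from an appointment", the text allows that, "with the patient's consent, a medical assessment may be completed by phone".
- **Measures to avoid dropouts.** After randomisation, "it will be necessary to minimize the dropouts in order to maintain the random effect of the randomization".
- **Statistics.** The analysis is by intention to treat, and expected dropouts are the stated reason. The primary comparison is the rate of complete resolution, by chi-square test.
- **Missing data.** Patients with many gaps are excluded; so are those "not including the data necessary to calculate the primary outcome will be excluded from the study".
- **Compliance bias.** More side effects, and possibly lower compliance, are expected on topiramate (TPM) than on levetiracetam (LEV).

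**The concern.** The trigger for removal is a treatment event: failing both drugs, or declining the second. It is not a decision to leave the research. A patient who has stopped but would still answer the month 6 phone questionnaire is removed by rule, whereas one who refuses to attend visits may still be assessed by phone.

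Those removed are not a random subset. They leave because symptoms persist or a drug was not tolerated, and the protocol expects tolerance to differ by arm. What is lost is their TNS status, episode frequency and duration, and the course of side effects at the remaining contacts. No later analysis can recover assessments that were never made. If the same patients also fall under the Missing data rule, failures can leave the denominator of the primary comparison in a trial with few patients per arm.

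**Working it through.** **1. Which assessments are at risk.** Contacts are at week 2 and months 2, 4 and 6 (Follow-up; Table 4). The offer of the other drug, and so the refusal or second failure that leads to removal, comes after 2 months. Months 4 and 6 are therefore chiefly at risk.

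**2. How many patients.** Sample size aims for 15 per arm, 30 in all, with a NESIS score of 4 or more, raised for 30-40% dropout or loss to 42. The stated figure is reproduced by 30 × 1.4 = 42, or 21 per arm. The expected loss is 0.30 × 42 = 12.6 to 0.40 × 42 = 16.8, about 13 to 17 patients. That is loss from all causes. The protocol gives no split, so the share due to this rule cannot be derived.

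**3. What happens if removed non-resolvers are also dropped from the analysis.** Let p be the true resolution rate and f the share of non-resolvers lost and dropped. Then

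apparent rate = p / [p + (1 − p)(1 − f)].

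The values of p and f below are assumptions; the documents give none for f. True resolution is equal in both arms.

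- f = 35% in both arms: p = 0.30 reads 0.30/0.755 = 0.40, and p = 0.50 reads 0.50/0.825 = 0.61. The difference is 0, but both rates are overstated.
- f = 50% TPM, 20% LEV: at p = 0.30, 0.30/0.65 − 0.30/0.86 = 0.462 − 0.349 = 0.113. At p = 0.50, 0.50/0.75 − 0.50/0.90 = 0.667 − 0.556 = 0.111.
- f = 60% TPM, 20% LEV: at p = 0.30, 0.30/0.58 − 0.349 = 0.168. At p = 0.50, 0.50/0.70 − 0.556 = 0.159.

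A simulation (200,000 runs, 21 per arm, uncorrected chi-square test, two-sided 5%) gave these type I errors at p = 0.30 and p = 0.50:

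- no loss: 0.055 and 0.046
- 35% and 35%: 0.054 and 0.052
- 40% TPM and 30% LEV: 0.059 and 0.058, with a false difference of about 0.04
- 50% and 20%: 0.105 and 0.103
- 60% and 20%: 0.158 and 0.156

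**4. One worked trial (assumed counts).** Nine of 21 resolve in each arm, 43% against 43%. Dropping 8 TPM and 2 LEV non-resolvers gives 9/13 = 69% against 9/19 = 47%. The gap of 22 points comes from the exclusions alone (p = 0.22).

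**5. The direction is not fixed.** At the planning rates, 14% on LEV and 100% on TPM, non-resolvers arise only on LEV. About 3 of 21 LEV patients resolve. If 6 LEV failures were dropped (an assumption), LEV would read 3/15 = 20% instead of 3/21 = 14%, which works against the trial's hypothesis.

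**The case against.** The strongest defence has four parts.

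- **The status on the assigned drug is already known at exit.** A patient who has failed both drugs has an observed non-resolution on the first, and data after a switch are kept out of the primary outcome anyway. Counting exits as not resolved could be set in a statistical analysis plan, and the bias in step 3 would then shrink. This stands for the primary endpoint. However, the protocol does not say that exits count as failures. A patient who stops for intolerance may have no TNS, and Other limitations mentions a favourable natural course, so status at exit need not be status at month 6. Frequency, duration and side effects after exit stay lost under any analysis rule.
- **The two follow-up rules cover different cases.** The phone assessment concerns missed or refused visits and is conditional on consent. That is correct, but it shows that the process needed for the fix already exists.
- **Safety is partly covered.** The follow-up form (Appendix 4) records discontinuation, its reason and graded side effects, and usual care continues. What ends is study recording of whether those effects persist or resolve.
- **Dose reduction and the switch offer themselves limit dropout.** They do, but only up to the point of removal.

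A reader might infer more than the text supports. That month 2 data are lost is doubtful, given the 2-month limit. That 13 to 17 patients are lost through this rule is not supported, as that is total loss. Nor can a count be built from all unresolved LEV patients (0.86 × 21 = 18): an unresolved patient who stays on the drug is not removed, and the documents give no refusal rate. Finally, the statements on reversibility under Risks of participating in the study do not show what patients are told, since the consent form is filed separately.

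**Conclusion.** The point holds. As written, stopping study treatment under this rule ends study follow-up without withdrawal of consent, chiefly at months 4 and 6, for a subset selected by persistent symptoms or intolerance. This is at odds with the dropout-limiting aim, the intention-to-treat statement and the phone route open to patients who miss or refuse visits.

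The effect on the primary result is conditional. It arises if these patients are also removed under Missing data. If those removed are mainly non-resolvers, resolution rates are then overstated, and unequal removal biases the comparison. False differences of about 0.11 to 0.17, with type I error of about 0.10 to 0.16, require assumed losses of 50-60% of TPM and 20% of LEV non-resolvers; equal losses give no false difference. The actual size is unknown because the protocol does not split the expected loss by cause, fixes no time point for the primary outcome and does not say how these patients count. That the primary result must be biased, or must favour TPM, is a tempting inference that the documents do not support.

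**What to change.** In Follow-up, replace the exclusion clause with wording to this effect: these patients leave study treatment but, unless they withdraw consent to follow-up, continue the remaining scheduled assessments to month 6, by phone if preferred, with TNS status, side effects and any new antiepileptic recorded. State that they stay in their randomised arm.

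Then reconcile three places so that they agree on who is followed and who is analysed: the Losses during follow-up paragraph, the stopping and switching paragraph (including the exclusion of post-switch data from the primary outcome), and Statistics with Missing data. Clinical care after stopping stays as the protocol states.

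The cost is a few extra phone assessments, using staff and a questionnaire already in place, and a matching sentence in the consent form if it needs one. No sample size changes.

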Then, we wanted to evaluate in a preliminary and retrospective way the incidence of this syndrome in the population of chronic SDH (cSDH). A descriptive and retrospective study aimed at comparing groups based on the NESIS score was then started. This study identified 22 patients from 2016 to 2018 who presented to the CHUS with TNS in the context of cSDH. Of these, 13 (59%) had a NESIS score of 4 or more. Particularly interestingly, and consistent with the initial hypotheses developed in relation to the existence and pathophysiology of NESIS, the NESIS and non-NESIS groups had significantly different responses to treatments. In fact, the response to standard antiepileptics (resolution of TNSs) was 100% in the non-NESIS group (probable epilepsy) compared to 14% in the NESIS group (p = 0.02, Fisher's exact test). In addition, 100% of patients in the

NESIS group who did not respond to standard antiepileptics responded with Topiramate or Lamotrigine (LTG) (2 antiepileptic treatments recognized for their impact on cortical depolarization) (article in process of submission, unpublished data)²⁸.

Following this preliminary study which described a significant difference in the response to treatment of TNS depending on the type of antiepileptic drug used and the NESIS score obtained, it is now more than relevant to validate this difference through a prospective randomized study. Indeed, a significant difference between the efficacy in the drugs studied and the NESIS groups would make it possible to offer a new therapeutic avenue for NESIS patients who do not seem to respond to usual treatments in addition to validating the existence of this new entity (NESIS). On the other hand, a better response to certain drugs known to have an incisive impact on cortical depolarization in the NESIS subgroup would strengthen the hypothesis of cortical depolarizations as a pathophysiological phenomenon underlying the NESIS entity. Prospective identification of these patients would also make it possible to better characterize the pathophysiology of symptoms.

Literature review

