In the retrospective study carried out at the CHUS by our research team²⁸, the results of which have not yet been published, the NESIS group had complete resolution of TNS in 14% when treated with usual antiepileptics. Upon failure of usual treatments and after a change to recognized treatments for cortical depression (Topiramate and Lamotrigine), 100% of patients had resolution of symptoms. It is important to understand that the treatment of the patients in this study was administered entirely within the hospital, a poorer compliance is therefore to be expected for our patients who will continue their treatment at home, which could affect the power of our study. However, these proportions are still those which come closest to what could be found in our study.

Calculation of sample size from proportions :

$$2N(by group) = \frac{4(z\alpha + z\beta)^2 \bar{p}(1 - \bar{p})}{(pc - pexp)^2}$$
$$2N(by group) = \frac{4(1,960 + 1,282)^2 0,57(1 - 0,57)}{(0,14 - 1)^2}$$
$$2N = 14$$
$$N = 7$$

The size calculated with the core studies as well as with the proportions taken in the retrospective study in our center are similar (8 and 7, respectively). In order to prevent a lack of potency for the reasons mentioned above, a slightly larger size will be preferred, and 15 patients seems a reasonable number. This calculation represents the sample size that one should aim for in each group (intervention and active comparator) within the

NESIS subgroup. It will therefore be necessary to analyze the results of nearly 30 patients in the NESIS group.

As the non-NESIS patients are not part of our primary outcome and are less numerous than the NESIS (72% compared to 28%²⁸), they will be included in the study without a specific target, up to a maximum of 30 patients and their results will be analyzed descriptively.

[figure not shown]
α = 0,05 by convention β = 0,10 by convention
β = 0,10 by convention
p = Mean proportion between 2 groups
((0,14+1)/2 = 0,57)
pc = comparator's proportion (14% = 0,14)
<pre>pexp = intervention's proportion (100% = 1)</pre>
Z = normalized form of the error according
to constant values without units

Considering the dropout or loss rate at follow-up,

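### The protocol fixes an unspecified chi-square test for about 12 to 15 analysed NESIS patients per arm; read as uncorrected it does not guarantee the stated 5%, and one exact test should be named in advance

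*Protocol*

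**What the plan says.** Protocol, Data analysis, Statistics: the primary outcome is complete resolution of symptoms (yes or no), compared between the two drugs, and "a Chi-Square test will be used". The section continues: "This same test will also be used to compare the response of TPM in the NESIS versus non-NESIS subgroups", with the same comparison repeated for LEV. Tolerance is also compared by chi-square. No continuity correction, exact test or small-count rule is given. For the Student's t-test, by contrast, the same section asks that the assumptions be checked first.

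Protocol, Degree of significance: "We retained a significance level corresponding to an error α of 5%, whether a value p<0.05". Also: "The accepted beta error (β) is 10%, for a power of 90" per cent.

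Protocol, Sample size: the target is 15 analysed patients per arm within NESIS. To allow for 30-40% loss, 42 NESIS patients are to be enrolled, among 56 in all. Non-NESIS patients have no specific target (maximum 30), are outside the primary outcome, and are to be reported descriptively.

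Protocol, Introduction: for its own small retrospective comparison the team reported "p = 0.02, Fisher's exact test".

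**The concern.** The chi-square test is a large-sample approximation. With 12 to 15 patients per arm its true type I error depends on the exact arm sizes and on the unknown common resolution rate, and can lie on either side of 5%. The trial declares 5%, so a positive result with p just under 0.05 would be open to challenge.

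The version matters as much as the sample size. At 15 per arm the uncorrected and continuity-corrected forms behave very differently, and the protocol does not say which one applies. If that is settled after the data are seen, a borderline verdict can turn on the choice.

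The within-drug NESIS versus non-NESIS tests use still smaller groups, and the Sample size section does not foresee any test for those patients.

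**Working it through.** **Plan's own figure.** 2N = 4 × (1.960 + 1.282)² × 0.57 × 0.43 / (0.14 − 1)² = 13.93, so 14 in all and 7 per group. This reproduces. The plan then raises 7 (and 8 from its means calculation) to 15 by judgement.

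**Analysed sizes (derived).**
- NESIS: 42 × 0.70 = 29.4, or 14 to 15 per arm; 42 × 0.60 = 25.2, or 12 to 13 per arm.
- Non-NESIS: 56 − 42 = 14, or 7 per drug; 7 × 0.70 = 4.9 and 7 × 0.60 = 4.2, so 4 to 5 after loss.

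**Method.** For arms n1 and n2, with x and y resolved, list every 2×2 table and mark those that the test rejects at two-sided 5% (uncorrected chi-square: statistic at least 3.841). For a common rate p,

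size(p) = Σ over rejected (x, y) of C(n1,x) C(n2,y) p^(x+y) (1−p)^(n1+n2−x−y).

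The maximum is taken over a fine grid of p. Power replaces p by the two arm rates.

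**Type I error, TPM v LEV in NESIS.**

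| Arms | Uncorrected, maximum | Uncorrected at p = 0.57 | Boschloo, maximum |
|---|---|---|---|
| 15 v 15 | 5.5% | 4.7% | 4.3% |
| 14 v 15 | 6.2% | 6.0% | 4.4% |
| 14 v 14 | 5.2% | 4.4% | 4.2% |
| 13 v 13 | 7.6% | 7.3% | 4.9% |
| 12 v 13 | 5.3% | 4.6% | 4.8% |
| 12 v 12 | 6.4% | 6.2% | 4.5% |

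The rate 0.57 is the plan's pooled proportion, (0.14 + 1)/2. At 15 v 15 the uncorrected test exceeds 5% only for common rates of about 0.20-0.38 and 0.62-0.80. At 13 v 13 it does so for about 0.25-0.75. With the continuity correction the maximum at 15 v 15 is 1.65%.

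**Power with LEV at 14%.**

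| TPM rate, patients per arm | Uncorrected | Unconditional exact | Corrected or Fisher |
|---|---|---|---|
| 100%, 15 | 1.000 | 1.000 | 1.000 |
| 70%, 15 | 0.914 | 0.904 | 0.82 |
| 60%, 15 | 0.785 | 0.751 | 0.62 |
| 50%, 15 | 0.599 | 0.542 | 0.39-0.40 |
| 70%, 13 | 0.907 | 0.854 | 0.81 |

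Barnard's and Boschloo's tests coincide at 15 v 15 and 13 v 13. The largest loss at 15 v 15 with LEV at 14% is 5.9 points, at a TPM rate near 47%.

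**Borderline tables.**
- 2/15 v 7/15: statistic = 30 × (2×8 − 7×13)² / (15×15×9×21) = 168,750/42,525 = 3.97, p = 0.046. With the correction, 30 × (75 − 15)² / 42,525 = 2.54, p = 0.111. Boschloo gives p = 0.055 and Fisher 0.109.
- 4/13 v 9/13: statistic = 26 × (16 − 81)² / 13⁴ = 109,850/28,561 = 3.846, p = 0.0499. Boschloo gives p = 0.076.

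**Within-drug subgroup tests, uncorrected maximum.** 15 v 7, 6.8%; 21 v 7, 6.2%; 15 v 5, 5.2%; 20 v 8, 4.8%; 13 v 4, 4.2%. At a rate of 0.57 the smallest expected count among 7 non-NESIS patients is 7 × 0.43 = 3.0. In an arm of 15 it is 15 × 0.43 = 6.5.

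**The case against.** The excess is small where the plan aims. At 15 v 15 it is at most half a point and absent at the pooled rate of 0.57, where expected counts also meet the usual minimum of 5. At the planned 100% v 14%, uncorrected and exact tests both have power 1.000, so only borderline tables change verdict. All of this stands, and it keeps the point modest.

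The protocol does not say Pearson or uncorrected. A reader might infer that an inflated test has been fixed; the text does not support that, because a corrected version would be conservative. What is fixed is a large-sample test of unstated version. A statistical analysis plan, not at hand, might settle the version. The protocol nevertheless makes the choice of test itself and applies it to every yes/no comparison, so the choice can be reviewed here.

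A reader might also cite 9.5% for a 15 v 4 subgroup split. That size mixes dropout assumptions: four non-NESIS patients per drug implies about 40% loss, which leaves about 13 NESIS patients rather than 15, and 13 v 4 peaks at 4.2%. The plan does not predict 15 v 4.

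Nor is the exact test almost free. At 13 per arm it brings power at 70% v 14% from 90.7% to 85.4%, and in the subgroups the loss can exceed 10 points. Part of the power lost is bought by exceeding 5%, but the cost is real. Finally, Fisher's test in the retrospective comparison does not bind this trial, and Fisher would cost about 10 points at 70% v 14% with 15 per arm.

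**Conclusion.** The point holds in moderate form. At the arm sizes that follow from the plan's own loss rate, the uncorrected chi-square does not guarantee 5%: its maximum is between 5.2% and 7.6% across the splits checked, and at the plan's pooled rate of 0.57 it is 6.0% at 14 v 15, 7.3% at 13 v 13 and 6.2% at 12 v 12. Three of the six splits (15 v 15, 14 v 14, 12 v 13) are at or below 5.5% at worst and below 5% at 0.57. If the corrected version is meant, the error runs the other way, to about 1.7% and about 82% power at 70% v 14%.

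This rests on loss being spread evenly between arms, on lost patients leaving the analysis (the Missing data section excludes those without primary-outcome data), and on the primary test being confined to NESIS, as the Sample size section implies. The Statistics section does not state that restriction; with all 56 analysed, 28 v 28, the uncorrected maximum is 5.4%.

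For the non-NESIS comparisons the firmer finding is the conflict between Statistics, which tests them, and Sample size, which describes them. The figure of 4 to 7 non-NESIS patients per drug is derived from 56 − 42 and is not stated in the protocol.

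**What to change.** In Statistics, replace the chi-square test for the primary outcome by one named unconditional exact test, Boschloo's or Barnard's, two-sided at 5%, for the TPM versus LEV resolution rate in NESIS patients. Report a matching exact confidence interval for the difference in rates. Choose between the two tests in advance, since they can differ when arms are unequal.

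For NESIS versus non-NESIS within each drug, reconcile Statistics with Sample size: either drop these tests and report descriptively, or use the same exact test labelled exploratory.

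The wording change is a line or two. The power cost is nil at the planned effect, about 1 point at 70% v 14% with 15 per arm and about 5 points with 13, and 3-6 points at 15 per arm if TPM resolves 45-60%. Software other than SPSS may be needed.
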